9.5 Secondary analyses

Safety analysis: The safety analysis will use the safety population. Adverse events will be summarized by grade, attribution, and system organ class.

Secondary efficacy analyses: Subjects will have clinical tumor measurement prior to initiating IPI-549 and after 2 weeks administration of IPI-549. Only clinical measurement of disease will be performed. If clinical assessment is not feasible, this will be indicated on the CRF with the reason.

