3. CMP: Comprehensive metabolic panel (bicarbonate, calcium, chloride, creatinine, glucose, potassium, sodium BUN, albumin, bilirubin total, alkaline phosphatase, total protein, ALT, AST).
4. Pregnancy test for females of child-bearing potential only.
5. Tumor tissue collection: See Section 6.1.8 for specifications.
6. Blood for correlative studies should be collected at the same time blood is drawn for CBC and CMP if possible. 40 mL blood to be collected at baseline; 30 mL blood to be collected at pre-surgery visits. See Section 6.1.8.
7. Scans will be performed when clinically indicated.
8. IPI-549 administration (Section 5.2): administered PO 40 mg QD until 24 hours prior to date when surgery is performed. Not allowed less than 24 hours of surgery.
9. In Follow-Up period, concomitant medications will be collected at Safety Follow-Up visit (approximately 30 (+7) days after the last dose of study drug) and for SADs. During this period, adverse events will be collected at Safety Follow-Up and SAEs until 90 days after last dose of study drug.
10. Surgery is to be performed no later than 48 hours after last dose of therapy. Therapy should continue until the day before surgery.
11. Tumor tissue collection to occur during surgery.

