3.2 Secondary Objectives

1. To measure changes in myeloid and T cell composition and activation status by immunohistochemistry and TCR sequencing.
2. To determine safety and tolerability of IPI-549 and change in tumor size in patients with locally advanced HNSCC.
3. To measure changes in peripheral cytokines and immune cells

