5.3 Duration of Study Treatment

IPI-549 for 2 weeks prior to surgical resection. Subjects will be monitored continuously for toxicity while on study therapy. Toxicity will be assessed using the NCI-CTCAE, v. 5.0 or higher. There will be no dose modification allowed on study. Missed doses should be recorded on the pill diary. Any grade 3 toxicity will result in discontinuation of IPI-549. If at any time 3 or more subjects have observed progression prior to the start of definitive treatment the study will be halted.

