7.1 Adverse Event Monitoring

Adverse event data collection and reporting, which are required as part of every clinical trial, are done to ensure the safety of subjects enrolled in the studies as well as those who will enroll in future studies using similar agents. Adverse events are reported in a routine manner at scheduled times during a trial. Additionally, certain adverse events must be reported in an expedited manner to allow for optimal monitoring of patient safety and care.

As far as possible, each adverse event should be evaluated to determine:

- duration (start and end dates)
- severity (grade)
- seriousness
- relationship to study agent
- action taken (i.e., none, study agent modification, medical intervention)
- outcome (i.e., resolved without sequelae, resolved with sequelae, ongoing)

Adverse events monitoring begins at the time of initiating study treatment through **90 days** following the last administration of study treatment or study discontinuation/termination, or the initiation of new anti-cancer therapy, whichever is earlier, whether or not related to IPI-549.

Note: Serious adverse events must be recorded in the case report forms for this 90 day-period; however, non-serious adverse events need only be recorded through 28 days post last study drug administration.

All patients experiencing an adverse event at least possibly related to study treatment will be monitored until:

- the adverse event resolves or the symptoms or signs that constitute the adverse event return to baseline;
- any clinically significant abnormal laboratory values have returned to baseline;
- there is a satisfactory explanation other than the study drug for the changes observed; or
- death.

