9.0 STATISTICAL CONSIDERATIONS

9.1 Study populations

The efficacy population will consist of all subjects who have received 2 weeks of study drug. Any subject who has not received 2 weeks of study drug will be replaced.

The safety population will consist of all subjects who have received any dose of study drug.

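### Section 9.5 does not separate adverse events before surgery from those after it, so post-operative events may dominate the all-cause safety tables and only investigator attribution tells drug from surgery

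*Combined protocol and SAP*

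**What the plan says.** Section 3.2 makes safety a secondary objective: "To determine safety and tolerability of IPI-549". Section 9.1 sets the analysis population: "The safety population will consist of all subjects who have received any dose of study drug". For the analysis itself, section 9.5 says: "Adverse events will be summarized by grade, attribution, and system organ class". Section 3.3 narrows the safety endpoint to events related to IPI-549. No section defines a pre-operative period or a treatment-emergent event.

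The timing comes from four places:

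- Section 5.3 sets the treatment period: "IPI-549 for 2 weeks prior to surgical resection".
- Schedule of Events, footnote 10: "Surgery is to be performed no later than 48 hours after last dose of therapy". Footnote 8 sets the other limit on the last dose: "Not allowed less than 24 hours of surgery".
- Section 7.1, serious events: "Serious adverse events must be recorded in the case report forms for this 90 day-period". Non-serious events: "non-serious adverse events need only be recorded through 28 days post last study drug administration". The same section closes monitoring sooner if new anti-cancer therapy begins.
- The Schedule of Events and section 5.4 place the safety visit about 30 days after the last dose, with blood count and chemistry repeated.

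Section 7.4 gives five attribution categories, from definite to unrelated, all judged against study treatment. Section 6.1.1 counts any change from screening as an adverse event and does not exempt expected post-operative changes.

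**The concern.** In a window study the drug is given for two weeks and a major operation follows almost at once. A reader of the safety results wants to know what happened on drug before surgery, whether recovery was unusual, and whether subjects finished the drug and reached surgery on time. The planned summary does not present the first two separately and gives no estimate for the third.

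The split by grade and organ class mixes pre-operative and post-operative events. The split by attribution rests on an investigator's judgment in an unblinded, single-arm trial. That judgment is hard here: section 8.1 lists anemia, nausea, vomiting, fatigue, fever and local swelling among the drug's side effects, and all are plausible after surgery too. Error can run either way, with surgical events credited to the drug or drug effects on recovery judged unrelated.

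Tolerability also leaves the analysis by another route. Section 5.3 stops the drug at any grade 3 toxicity, and sections 9.1 and 9.3 replace subjects who do not complete two weeks. The primary analysis then omits them, and no planned summary says how many there were.

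**Working it through.** The plan gives no figure for event counts or for the post-operative share of the window, so there is none to reproduce. Its power statement concerns the primary endpoint and is not touched by this point.

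**Inputs.** On-drug period 14 days (5.3). Gap g from last dose to surgery 1 or 2 days (Schedule of Events, footnotes 8 and 10). Post-dose recording window W = 28 days for non-serious events and 90 days for serious events (7.1). The first calculation assumes that resection does not close the window.

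**Share of days.** Post-operative days = W − g. Share of post-dose time = (W − g)/W. Share of the whole window = (W − g)/(14 + W).

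| Events | W | g | Post-operative days | Share of post-dose time | Share of whole window |
|---|---|---|---|---|---|
| Non-serious | 28 | 1 | 27 | 27/28 = 96.4% | 27/42 = 64.3% |
| Non-serious | 28 | 2 | 26 | 26/28 = 92.9% | 26/42 = 61.9% |
| Serious | 90 | 1 | 89 | 89/90 = 98.9% | 89/104 = 85.6% |
| Serious | 90 | 2 | 88 | 88/90 = 97.8% | 88/104 = 84.6% |

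If collection in fact runs to the safety visit at 30 to 37 days, the share of post-dose time is 28/30 = 93.3% to 36/37 = 97.3%, so the picture is the same.

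**If resection closes the window.** The window is then 14 + g = 15 or 16 days, and the post-operative share is zero.

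**From days to events.** This needs event rates, which the documents do not give. Let r be the assumed ratio of the post-operative to the pre-operative daily event rate. The post-operative share of events is r(W − g)/[r(W − g) + 14 + g].

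| r (assumed) | Non-serious | Serious |
|---|---|---|
| 0.25 | 29–31% | 58–60% |
| 0.5 | 45–47% | 73–75% |
| 1 | 62–64% | 85–86% |
| 2 | 77–78% | 92% |
| 5 | 89–90% | 97% |

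Half of all events are post-operative when r = (14 + g)/(W − g). That is 15/27 = 0.56 to 16/26 = 0.62 for non-serious events, and 15/89 = 0.17 to 16/88 = 0.18 for serious events. Post-operative events form the majority unless the daily rate after surgery is clearly lower than the rate on drug.

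**Precision of the missing tolerability estimates.** The safety population is everyone dosed, so its size exceeds 15 as soon as anyone is replaced. If three subjects do not complete and are replaced until 15 have completed, the proportion is 3/18 (16.7%; 95% Clopper-Pearson interval 3.6–41.4%), not 3/15 (20%; 4.3–48.1%). With no non-completers, 0/15 gives 0–21.8%. Because dosing continues until 15 complete, the number dosed is not fixed in advance, and the binomial interval for completion is only approximate.

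**The case against.** The strongest reply is that events are not simply pooled. Section 9.5 breaks them down by attribution, and the declared endpoint in section 3.3 is related events. A surgical event judged unrelated does not enter that endpoint, yet stays visible in the summary. A reader might infer that surgical events will swamp the drug's profile, or that drug-related surgical complications will be lost. The documents support neither: they give no event rates, the non-serious share ranges from about 29% to 90% over the ratios assumed above, and unrelated events are still tabulated. This part of the reply stands.

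Second, section 7.1 ends monitoring at new anti-cancer therapy, and section 9.4 calls the operation definitive treatment. If resection counts, there is almost no post-operative window. If it does not, later anti-cancer therapy can still shorten the 28 or 90 days. The 28/90-day note and the 30-day visit suggest that collection was meant to continue, but the text does not settle it. The day shares are therefore conditional, and upper values.

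Third, a split at surgery cannot show an excess of surgical complications without a control group. That is correct; the split improves what can be read about the on-drug period and does no more.

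Fourth, section 7.1 already seeks start and end dates and the schedule has an assessment before surgery, so the split could be made at reporting. That shows that it is cheap, not that it is planned.

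Attribution nevertheless remains the only planned separator, whereas onset relative to surgery is a matter of dates.

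**Conclusion.** The point holds as a reporting gap in a secondary, descriptive analysis. No period split is planned. If surgery comes 1 to 2 days after a full 14 days of drug and resection does not end monitoring, about 62–64% of the non-serious window and 85–86% of the serious window lies after surgery. Post-operative events may therefore dominate the all-cause tables; whether they do depends on rates that the documents do not give, and nothing shows that they would dominate the table of related events.

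Non-completion and surgical delay have no planned estimate. Section 9.4 counts delays only as a stopping trigger, and only those put down to drug-related events; it should not be read as already supplying a count of all delays. Nothing here alters sample size, alpha, power or a decision rule. The change is worth making because it allows the trial to answer its own safety and tolerability objective at little cost.

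**What to change.** 1. In section 9.5, tabulate adverse events by onset in two periods: first dose to start of surgery, as the main tolerability table, and after surgery, showing all events whatever the attribution. Keep the present summary as the total. State how subjects who never reach surgery are assigned.
2. Reconcile the early-closing clause in 7.1, its 28/90-day note and the 30-day visit, and state whether resection ends collection. The Schedule of Events should also be made consistent on the interval from last dose to surgery: the line above the footnotes, footnote 8 and footnote 10 do not agree. This note takes no view on which interval is right.
3. Report, in the safety population with its actual denominator, the proportion not completing two weeks of drug and the proportion whose surgery was delayed by at least a week, the latter both for any cause and as defined in 9.4. Give 95% Clopper-Pearson intervals, described as approximate for completion because non-completers are replaced.

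The cost is SAP wording and a few extra tables. Event start dates are already sought in 7.1. The one further requirement is that the originally planned surgery date be recorded as well as the actual date, since delays cannot be counted without it.

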5.5 Discontinuation from Study Participation

Patients may be removed from study participation for the following reasons (in addition to those listed for discontinuation of study treatment):

- The patient or legal representative withdraws consent for follow-up;
- The patient is lost to follow-up;
- The patient dies;
- It is the decision of the investigator.

- Severe allergic or anaphylactic reaction to IPI-549
- Disease progression prior to surgery
- Pregnancy
- Severe or life-threatening toxicity

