9.2 Study Design/Study Endpoints

We anticipate enrolling 15 subjects. The primary analysis will use the efficacy population. Within subject change from the post-treatment to the pre-treatment sample in the immune activation signature will be the primary endpoint. We will test the hypothesis of an increase in this signature using a one sided paired t-test at 5% significance level. With 15 subjects we have 80% power to detect a difference in the mean signature equal to 0.68 standard deviations, which is a modest effect size. Although we lack preliminary data on the magnitude of the standard deviation of within subject changes, effect sizes less than this would be unlikely to be clinically interesting. Also, the differences seen between the poor prognosis and good prognosis groups in Kaneda et al. [2] were greater than this minimal effect size. Thus the study appears to be well-powered to detect meaningful differences.

[figure not shown]

Figure 1: Illustration of shift in the signature distribution, which would yield an effect size of 0.68

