9.3 Sample Size and Accrual

We anticipate enrolling 15 subjects. Subjects who do not complete 2 weeks of IPI-549 therapy will be replaced. Thus far, IPI-549 in advanced cancer patients has been well tolerated without serious toxicity. Therefore, we anticipate being able to fully accrue this trial within one year of activation and the administration of IPI-549 will not interfere with planned surgery. If at any time 3 or more subjects have observed progression prior to the start of definitive treatment the study will be halted.

Accrual Targets			
Ethnic Category	Sex/Gender		
	Females	Males	Total
Hispanic or Latino	1	2	3
Not Hispanic or Latino	4	8	12
Ethnic Category: Total of all subjects	(A1)	(B1)	(C1)
Racial Category			
American Indian or Alaskan Native	0	0	0
Asian	1	1	2
Black or African American	1	1	2
Native Hawaiian or other Pacific Islander	0	0	0
White	3	8	11
Racial Category: Total of all subjects	(A2)	(B2)	(C2)

(A1 = A2) (B1 = B2) (C1 = C2)

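### A subject who stops IPI-549 before 2 weeks, for progression or grade 3 toxicity, has no scheduled post-treatment tumor measurement and can drop out of the descriptive tumor-size result

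*Combined protocol and SAP*

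**What the plan says.** Section 3.2 includes change in tumor size in secondary objective 2. Section 9.5, under secondary efficacy analyses, gives the timing: "Subjects will have clinical tumor measurement prior to initiating IPI-549 and after 2 weeks administration of IPI-549". Measurement is clinical only, and where it is not feasible the reason goes on the CRF.

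Two populations are defined in 9.1. For efficacy: "The efficacy population will consist of all subjects who have received 2 weeks of study drug". The safety population is everyone dosed. Section 9.1 adds "Any subject who has not received 2 weeks of study drug will be replaced", and 9.3 repeats it: "Subjects who do not complete 2 weeks of IPI-549 therapy will be replaced". Section 9.2 assigns a population to one analysis only: "The primary analysis will use the efficacy population".

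There are two main routes to an early stop. Section 5.5 begins "Patients may be removed from study participation for the following reasons" and lists "Disease progression prior to surgery" among them. Sections 5.3 and 9.4 require IPI-549 to be discontinued for any grade 3 toxicity.

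The Schedule of Events has no tumor-measurement row and no visit between Day 1 and Day 14 (±3 days). Exams after baseline are targeted, and note 7 reads "Scans will be performed when clinically indicated". Section 9.4 halts the study once 3 or more subjects have progressed before definitive treatment, with formal review at least bi-annually.

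**The concern.** The second tumor value depends on completing 2 weeks of drug, and one reason for not completing is that the tumor has grown. Take a subject whose progression is noticed at an unscheduled contact on day 8 and who then stops. The plan calls for no post-treatment measurement, and another subject takes the place. A subject who stops on day 8 for grade 3 toxicity loses the value in the same way.

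If early progressors are missing, the tumor-size result describes those who stayed on drug and looks better than the experience of everyone treated. There is no control arm against which that would show. Other parts of the plan do not clearly fill the gap. Section 9.5 plans no summary of progression, 7.0 keeps progression out of the adverse events unless it is judged drug related, and 10.4 reports response for evaluable patients without defining the term. A value not taken before definitive treatment cannot be recovered.

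**Working it through.** **The plan's own figure.** The only power statement is in 9.2: 80% for the primary signature test with n = 15, an effect of 0.68 SD and a one-sided paired t-test at 5%. From the noncentral t with 14 df and noncentrality 0.68 × √15 = 2.63, power is 80.5%, so the figure reproduces. No power is given for tumor size, and nothing below changes the 15 or the 80%.

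**Can the value go missing if the plan is followed as written?**

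| Place | What it provides | Tumor measurement at an early stop? |
|---|---|---|
| 9.5 | Baseline and after 2 weeks | No |
| 9.5, CRF sentence | Reason recorded if assessment is not feasible | No; covers infeasible assessments |
| 6.0 | Monitoring at early discontinuation | No; for safety and tolerability |
| 6.1.7 | ECG at a treatment termination visit | No; ends in two stray words on tumor assessment, with no content |
| 5.4 | 30-day visit with physical exam | No; the tumor may already be resected |
| Schedule of Events | Day 14 ±3 visit, targeted exam | No tumor row; a subject stopping on days 11 to 13 could still be seen in the window |

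No row schedules the measurement, so the value can go missing.

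**How many progressors can this affect?** Inputs: 15 completers (9.2, with replacement under 9.1 and 9.3) and a halt at 3 progressions (9.4).

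- Largest number of progressors in a trial that is not halted: 3 − 1 = 2.
- Subjects dosed if both stop early and are replaced: 15 + 2 = 17.
- Share without a scheduled post-treatment value: 2/17 = 11.8%, exact (Clopper-Pearson) 95% CI 1.5% to 36.4%.
- If only one: 1/16 = 6.3%, exact 95% CI 0.2% to 30.2%.

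If no completer progresses, a completers-only account would show 0/15, while the dosed subjects give 1/16 or 2/17.

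**Where that bound stops.** A halted trial could contain three, or more if progressions build up between formal reviews. Toxicity stoppers are outside the bound: the other rule in 9.4 counts only surgery delayed by a week or more for related events, so a grade 3 stopper whose surgery is on time counts toward neither rule. Their number cannot be estimated. Section 8.1 reports grade 3 or higher events in 5 of 12 phase 1 subjects, but in advanced disease, at 10 to 30 mg, and without stating the exposure time.

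**The case against.** The best case against this has four parts.

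1. **An observed progression implies that someone examined the tumor.** A day-8 progressor may well have an informal assessment. That stands. It makes the fix easier, but it does not put the value into the planned data: 9.5 does not ask for it, and no measurement day need be recorded.

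2. **The chain is optional.** Removal for progression is discretionary, and a progressor who completes 2 weeks is measured and kept. This stands for progression, but not for grade 3 toxicity, where stopping is mandatory.

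3. **Nothing is hidden.** A reader might infer that the plan excludes early progressors or conceals their events. The documents do not support that. Section 9.5 names no population for tumor size, 9.2 ties the efficacy population to the primary analysis only, and 9.4 counts all progressions and reviews the rule in a formal safety report.

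4. **The stakes are low.** Tumor size is not a numbered secondary endpoint in 3.3 and has no test, power or decision threshold. This stands.

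A reader might also want a size of bias or a probability. The documents support neither. A mean shift would need an assumed growth figure and a mean that 9.5 never plans. The chance of one or two replaced progressors rests wholly on an assumed early-progression rate: 49% at 5% and 56% at 10% if no completer ever progresses, but 35% and 22% if completers progress at the same rate, because the study then halts more often.

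**Conclusion.** The gap is real and its consequences are small. As written, a subject who stops IPI-549 before 2 weeks has no scheduled post-treatment tumor measurement and is replaced, so tumor-size data can be missing for a reason tied to tumor growth or to toxicity.

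The size that can be stated is a count: at most two progressors in a trial that is not halted, 2 of 17 dosed (11.8%, exact 95% CI 1.5% to 36.4%). This assumes that 15 subjects complete, that both progressors stop early and that the halt operates at the third progression. Two is not a ceiling on all missing values, since toxicity stoppers and a halted trial fall outside it.

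The point concerns the descriptive tumor-size result only; it makes no claim about the primary signature test. It is a cheap improvement to the plan, not a flaw that undermines it.

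**What to change.** Add to 9.5:

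1. When IPI-549 is stopped early for any reason, take a dated clinical tumor measurement before definitive treatment.
2. Report progression before definitive treatment as n/N of all dosed subjects with an exact 95% CI, counting early progressors whether or not they were measured. The numerator is already tracked for 9.4.
3. List each dosed subject's tumor change with its measurement day, including replaced subjects.
4. Label any 2-week summary as completers-only.

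The cost is a few sentences and one clinical measurement per early stopper. It needs no extra subjects and no scans. The downside is that measurement days will differ between subjects, for example day 8 against day 14, so the changes should be listed by subject and not pooled into one all-dosed mean.
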